### **Missing Data**

The impact of missing data due to loss to follow-up prior to completing both arms will be assessed by sensitivity analyses using several methods of imputation including multiple imputations for the primary performance and primary safety endpoints. Details will be specified in a separate statistical analysis plan.

# Vapotherm, Inc

## MODERATION Neo – Maintaining Optimal DEliveRy Using Automatic TItration of OxygeN Neonatal

Confidential

### **Poolability**

A poolability analysis will be performed to assess the poolability of sites with respect to the primary performance endpoint measure in the mITT subjects. A Student's t-test will be used to test for a difference in performance across sites. A significance level of 0.15 will be used to determine whether the sites are poolable. If a significant difference is found between sites, additional analyses will be done to identify factors that may be associated with this difference. Additionally, if a significant difference is observed, a random site adjusted estimate of the performance endpoint, along with 95% CI, will be provided.

Although enrollment will be monitored in an effort to strive for even allocation between sites, for purposes of the poolability analysis those sites with less than five (5) evaluable patients enrolled will be combined into a pseudo-site for purposes of analysis.

### **Primary Safety Objective**

Objective: To demonstrate that safety is not worse than standard practice. Specifically to demonstrate that the Vapotherm OAM, used in conjunction with the Vapotherm Precision Flow Hi-VNI to treat infants with heated, humidified high velocity nasal insufflation (HVNI), is not inferior to standard practice for time that infants' arterial blood oxygen saturation exceed or drop below a target range, thus minimizing the proportion of time the subject is exposed to elevated or reduced levels of oxygen in the inspired gas.

Endpoint: There are two safety endpoints: the proportion of time spent above the target SpO2 range and the proportion of time spent below. The proportion of time expressed as a percentage will be measured by pulse oximetry (SpO2), abstracting and analyzing recorded data over two contiguous 24-hour study periods; one 24-hour period with automated control (OAM) and one 24-hour period with manual control.

Subjects to Analyze: Subjects in the mITT cohort will be the primary analysis. Additional supplemental analyses will repeat this analysis using the FAS, the PP and Challenge cohorts. This will be used to provide an Adverse Event(s) summary.

#### Hypotheses:

Non-inferiority, proportion of time above range:

Ho:  $D \geq \delta$

Ha:  $D < \delta$ ,

where D = difference in proportion of time above range (OAM – standard practice) and  $\delta$  is the non-inferiority margin of 5.

Non-inferiority, proportion of time below range:

Ho:  $D \geq \delta$

Ha:  $D < \delta$ ,

where D = difference in proportion of time below range (OAM – standard practice) and  $\delta$  is the non-inferiority margin of 5.

# Vapotherm, Inc

## MODERATION Neo – Maintaining Optimal DEliveRy Using Automatic TItration of OxygeN Neonatal

Confidential

If both of the non-inferiority tests below reject the null and conclude non-inferiority is achieved, we will test for superiority.

Superiority, proportion of time above range:

Ho:  $D \geq 0$

Ha:  $D < 0$ ,

where D = difference in proportion of time above range (OAM – standard practice)

Superiority, proportion of time below range:

Ho:  $D \geq 0$

Ha:  $D < 0$ ,

where D = difference in proportion of time below range (OAM – standard practice)

Analysis Method: The difference (OAM – standard practice) of the proportion of time in range will be tested using a paired t-test using a one-sided alpha of 0.025 to test non-inferiority. If both are passed, testing for superiority will be performed again using a one-sided alpha of 0.025. Both superiority tests must be passed in order to claim superiority.

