#### Hypothesis:

Ho:  $D \leq 0$

Ha:  $D > 0$ ,

Where D = difference in proportion of time in range (OAM – standard practice)

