# Vapotherm, Inc

## MODERATION Neo – Maintaining Optimal DEliveRy Using Automatic TItration of OxygeN Neonatal

Confidential

Analysis Method: The difference (OAM – standard practice) of the proportion of time in range will be tested using a paired t-test using a one-sided alpha of 0.025.

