#### *Safety co-Endpoints – Time Above Target Range and Below Target Range:*

The safety co-endpoints will be powered to detect superiority even though we will first test for non-inferiority. The change in proportion of time SpO2 was above and below range was

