# Vapotherm, Inc

## MODERATION Neo – Maintaining Optimal DEliveRy Using Automatic TItration of OxygeN Neonatal

Confidential

$-15.0\% \pm 16.2\%$  and  $-12.6\% \pm 10.8\%$ , respectively. Using the largest standard deviation of 16%, again using PASS 14, a sample size of 38 will be adequate with at least 95% power for each test with a one-sided alpha of 0.025 to detect a difference as small as 10%. Both safety endpoints are powered at 95% ensure overall power is at least 90%.

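### The Analysis Method for the primary safety objective tests time in range, but the safety endpoints are time above range and time below range

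*Combined protocol and SAP*

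**What the plan says.** All references are to Section V of the combined protocol and SAP.

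- **Primary Safety Objective, Endpoint:** "There are two safety endpoints: the proportion of time spent above the target" range, and the proportion of time spent below it.
- **Primary Safety Objective, Hypotheses:** two non-inferiority hypotheses (H0: D ≥ 5 against Ha: D < 5), then two superiority hypotheses (H0: D ≥ 0 against Ha: D < 0). In each pair one D is time above range ("where D = difference in proportion of time above range (OAM – standard practice") and the other is time below range.
- **Primary Safety Objective, Analysis Method:** the difference (OAM minus standard practice) "of the proportion of time in range will be tested using a paired t-test using a one-sided alpha of 0.025 to test non-inferiority". The paragraph then makes superiority testing conditional on both being passed and ends "Both superiority tests must be passed in order to claim superiority".
- **Primary Performance Objective, Hypothesis and Analysis Method:** "Where D = difference in proportion of time in range (OAM – standard practice", with the difference "of the proportion of time in range will be tested using a paired t-test using a one-sided alpha of 0.025".
- **Opening text of Section V:** secondary endpoints are tested for possible labeling claims only if both safety non-inferiority endpoints and the performance endpoint are passed.
- **Sample Size Calculations, Safety co-Endpoints:** "The safety co-endpoints will be powered to detect superiority even though we will first test for non-inferiority". The calculation uses the above-range and below-range differences, "with at least 95% power for each test with a one-sided alpha of 0.025".

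**The concern.** The sentence quoted from the safety Analysis Method is the only one that assigns a statistical test to the primary safety objective, and it names the performance variable. Its wording matches the performance Analysis Method up to the alpha level, which suggests text carried over from there.

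Two things are at stake. First, the prespecified method for a primary safety test is ambiguous, and that test is part of the gate to the labeling claims. Second, a single in-range test could not do the job of the two safety tests. Time in range falls only when time above and time below rise in total, so a device that removes hyperoxia while adding hypoxia can look acceptable or better.

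The Background section gives a reason to keep the two sides apart. In a cited crossover study of another closed-loop system in ventilated preterm infants, range maintenance improved but time at SpO2 80% to 86% increased. That band lies wholly below this trial's 90% to 95% range.

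**Working it through.** **1. Which variable each part of the plan uses**

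| Place in Section V | Variable |
|---|---|
| Safety Endpoint | above; below |
| Safety non-inferiority hypotheses (margin 5) | above; below |
| Safety superiority hypotheses | above; below |
| Gate to secondary endpoints | both safety non-inferiority endpoints |
| Safety sample size | above; below |
| **Safety Analysis Method** | **in range** |
| Performance hypothesis and method | in range |

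The safety Analysis Method is the only safety entry that names time in range. The Missing Data section defers only missing-data details to a separate SAP, so the supplied text does not hand this test to another document.

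**2. The plan's safety sample size reproduces from the above/below inputs**

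Inputs from Sample Size Calculations: SD 16, difference 10, one-sided alpha 0.025, at least 95% power, stated n = 38.

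- Paired t-test, noncentrality = 10 / (16/√38) = 3.85, giving power 0.963 at n = 38.
- The smallest n reaching 95% is 36 by the plain paired t-test. Dividing by 0.955, an assumed efficiency for a nonparametric adjustment, gives 36/0.955 = 37.7, so 38.

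The design was therefore sized on the correct variables.

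**3. The sentence read literally**

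The only stated non-inferiority hypothesis form is H0: D ≥ 5 against Ha: D < 5. The pilot in-range difference is +28.4 (SD 10.8, Table 1). Applied to time in range with n = 40, that form would be rejected with probability essentially 0, because more time in range is a benefit. A sensible in-range test needs the opposite direction and a negative margin, and the plan states neither.

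**4. What an in-range test would miss (illustration)**

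Assumed, not in the plan: mean differences (OAM minus manual) of -15 above, +8 below and +7 in range, which sum to zero; and an in-range margin of -5, mirroring the plan's 5. From the plan: n = 40, one-sided 0.025, so critical t(39) = 2.023. SD 11 is the plan's rounded in-range value; 10.8 and 16.2 are the smallest and largest difference SDs in Table 1.

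- In range against -5: noncentrality = (7 + 5)/(SD/√40).
- Below against 5: noncentrality for rejection = (5 - 8)/(SD/√40).

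| SD | In-range noncentrality | P(in-range passes) | Below-range noncentrality | P(below-range passes) |
|---|---|---|---|---|
| 11 | 6.90 | >0.999 | -1.72 | 0.00013 |
| 16.2 | 4.68 | 0.995 | -1.17 | 0.00096 |

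The above-range test against 5 passes with probability above 0.999 at both SDs.

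Varying the assumptions, with above held at -15:

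| Below / in range | SD | P(in-range passes) | P(below-range passes) |
|---|---|---|---|
| +6 / +9 | 10.8 | >0.999 | 0.0057 |
| +6 / +9 | 16.2 | 0.9996 | 0.0096 |
| +10 / +5 | 10.8 | 0.9999 | <0.00001 |
| +10 / +5 | 16.2 | 0.968 | 0.00006 |

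**5. Redundancy with the performance test**

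The performance test passes when mean - 2.023 × SE > 0. Then mean - 2.023 × SE > -5 as well, and the same holds for any negative margin. On the same data, passing performance already implies passing in-range non-inferiority, so such a test adds no safety information.

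**Caveat.** The illustration treats the three categories as exclusive and exhaustive. The Table 1 means sum to 76.0 + 13.5 + 14.4 = 103.9 (automated) and 47.6 + 28.5 + 27.0 = 103.1 (manual), so the pilot categories are not exactly so.

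**The case against.** The strongest reply is that this is a recoverable wording slip. The endpoints, all four hypotheses, the margin and the gate point to one reading, and the same paragraph speaks of both tests, which cannot describe a single in-range test. An analyst who ran an in-range test would have to set aside four written hypotheses and invent a margin and direction. The gate also refers to both safety endpoints, so on its own terms it would not run on time in range. All of this stands, and it is why the point concerns a wrong variable in operative text and not a missing test.

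The illustration can also be challenged:

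- **Assumed effects.** They were chosen so that the two tests disagree. The pilot shows -15.0 above and -12.6 below (n = 18), and both weight groups in Table 2 favour the device on both sides. That is correct: the figures show what an in-range test could miss and do not predict harm.
- **SD of 16.2.** It is the above-range value; Table 1 gives 10.8 for both the in-range and below-range differences. That is fair, but the conclusion is the same at 10.8.
- **The cited closed-loop study.** It concerns another device in ventilated infants, and the Background does not report its total time below range. It serves only as an analogy.

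None of this corrects the sentence. The paragraph names one variable and then refers to two tests, and no other text resolves the conflict.

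**Conclusion.** The concern holds. The Analysis Method for the primary safety objective names time in range, although every other part of the plan that deals with safety testing uses time above and time below range. Followed literally, it gives no complete test and examines neither safety endpoint. Reading the plan as a whole recovers the intended tests, so the design itself is not at fault: the sample size, alpha, margin and power are unaffected.

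It should be fixed because it is the stated method for a primary test that gates labeling claims. The textual conclusion needs no assumptions. The size of the possible masking does: for below-range increases of 6 to 10 points with above-range time falling by 15, SD 10.8 to 16.2 and an assumed in-range margin of -5, the in-range test passes with probability 0.968 or more, and the plan's below-range test passes with probability at most 0.0096.

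**What to change.** Replace the Analysis Method paragraph under Primary Safety Objective with wording such as:

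> The differences (OAM - standard practice) in the proportion of time above range and in the proportion of time below range will each be tested by a paired t-test against the margin of 5 percentage points at one-sided alpha 0.025. Both null hypotheses must be rejected to conclude non-inferiority. If both are rejected, the same two differences will each be tested against 0 by a paired t-test at one-sided alpha 0.025; both must be passed to claim superiority.

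This uses only the variables, margin and alpha already in the plan. The cost is rewording one short paragraph, with no effect on data collection, sample size, alpha, margin or power. It should be done before the data are analysed, so that there can be no dispute about which variables were prespecified for primary safety.

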# Vapotherm, Inc

## MODERATION Neo – Maintaining Optimal DEliveRy Using Automatic TItration of OxygeN Neonatal

Confidential

testing will be used to test the secondary objective(s). If both primary safety non-inferiority endpoints are passed and the primary performance endpoint is passed, we will test the secondary endpoint(s) for potential labeling claims. Analyses will be performed using SAS version 9.2 or higher, or comparable statistical software. Data from technically compromised data collection shall not be included in the analysis but will be described in detail if there are any instances.

*Technical Definition of Analyzed Target Range* – To be in line with common practice, for all data analyses the term ‘target range’ is defined as an  $\text{SpO}_2=90\%-95\%$  or an  $\text{SpO}_2=90\%-100\%$  if  $\text{FiO}_2=0.21$ . The analyzed targeted oximetric blood oxygen saturation range denoted as ‘target range’ in the safety performance, primary performance, secondary performance, and additional objectives/analyses is defined here, to include those babies who are not hypoxic ( $<90\% \text{ SpO}_2$ ) whilst on room air ( $\text{FiO}_2=0.21$ ). Thus, at  $\text{FiO}_2=0.21$ , an  $\text{SpO}_2=90\%-100\%$  is deemed within target range. These are not clinically deemed ‘out of target range’ when  $\text{FiO}_2=0.21$  (at air, Eupoxia), even when the  $\text{SpO}_2$  is greater than 95%. This definition of the analyzed target range does not change the clinical practice, as clinicians still target babies to a target range of  $\text{SpO}_2=90\%-95\%$  by adjusting  $\text{FiO}_2$  accordingly.

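### Safety superiority and the secondary labelling claims each use the full one-sided 0.025, with no order or split between them, so the chance of a false claim across the two is bounded only by 0.05

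*Combined protocol and SAP*

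**What the plan says.** Three parts of Section V bear on this.

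- **Primary Safety Objective (hypotheses and analysis method).** If both non-inferiority tests "reject the null and conclude non-inferiority is achieved, we will test for superiority". The level is not reduced: "testing for superiority will be performed again using a one-sided alpha of 0.025". A claim rule follows: "Both superiority tests must be passed in order to claim superiority". Neither the performance test nor the secondary objectives are mentioned.
- **Opening paragraphs of Section V.** Hierarchical testing is applied to the secondary objectives. The condition for opening them is: "If both primary safety non-inferiority endpoints are passed and the primary performance endpoint is passed". Their purpose is potential labelling claims. Safety superiority is not named.
- **Secondary Performance Objectives 1 and 2.** Each is tested at one-sided 0.025, with a Hochberg adjustment across its own two groups (weight; light or dark skin).

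Sample Size Calculations adds that the safety endpoints are powered for superiority, not only for non-inferiority.

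**The concern.** The plan takes visible steps to limit multiplicity: a hierarchy ahead of the secondaries and Hochberg within each of them. Safety superiority sits outside that structure. It has hypotheses, a level, a claim rule and its own power calculation, so it cannot be treated as descriptive.

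The non-inferiority results therefore pass the same 0.025 on twice, once to safety superiority and once (with the performance test) to the secondaries. A false superiority claim and a false subgroup claim are two separate chances of error. At stake is whether those further claims can be defended as multiplicity-controlled. The primary non-inferiority and performance conclusions are not affected.

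**Working it through.** **The plan's own figure.** For safety superiority the inputs are difference 10, SD 16, one-sided alpha 0.025 and power 95%.
- Normal approximation: (1.960 + 1.645)² × 16² / 10² = 33.3, so 34.
- Exact paired t: 36.
- With the nonparametric adjustment that the plan names for the performance endpoint: 36 × π/3 = 37.7, so 38, as stated.
- Joint power for the two tests: at least 1 − 2 × 0.05 = 0.90, as stated.

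The superiority step is thus a planned, sized test.

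**Each branch alone.**
- Safety superiority: both tests must pass, so its error is at most 0.025. The non-inferiority gate does not reduce this, because an upper confidence limit below 0 is also below the margin of 5.
- One secondary objective: if one group truly benefits and the other does not, Hochberg tests the null group at up to the full 0.025.

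**Both branches.** The bound is 0.025 + 0.025 = 0.05. If independent, 1 − 0.975² = 0.0494.

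**How close the plan comes.** The written procedure was simulated with paired t-tests, 60,000 trials and n = 40. The change in time in range was set to minus the sum of the changes above and below range.
- From the documents: n = 40; margin 5; SDs of the paired difference 16.2 (above), 10.8 (below) and 10.8 (in range) from Table 1.
- Correlation implied by those SDs: 10.8² = 16.2² + 10.8² + 2ρ(16.2)(10.8), so ρ = −262.44 / 349.92 = −0.75.
- Assumed: normal differences; weight groups of 23 and 17; no change in time below range; no effect in the heavier group; 20 points less time above range in the lighter group.

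| SDs above / below (ρ = −0.75) | False safety superiority | False heavier-group claim | Either |
|---|---|---|---|
| 16.2 / 10.8 (Table 1) | 1.9% | 1.9% | 3.7% |
| 10 / 7 (assumed) | 2.4% | 2.5% | 4.9% |

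The two errors hardly overlap, so they almost add. With safety superiority required before the secondaries, the chance of either is 1.8–2.6%.

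A second set of runs (200,000 each) used a 60-point benefit in the responding group and correlations from −0.9 to 0. It gave 4.0–4.6% at Table 1 SDs and 4.6–5.0% with an SD of 8 or less for the null endpoint. Part of the gap is the non-inferiority gate: at zero true difference and n = 40 it passes only 48% of the time with SD 16.2 and 81% with SD 10.8, against 97% with SD 8.

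**Probability that the superiority step passes (n = 40).**
- Pilot effects: 99.99% for above range (−15.0, SD 16.2) and higher for below range (−12.6, SD 10.8), so about 99.99% jointly.
- Planned difference of 10 with SD 16: 97.1% per test; 0.971² = 0.943, and not below 2 × 0.971 − 1 = 0.942. About 94%.

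**The case against.** The strongest reply has four parts.

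1. **Moving from non-inferiority to superiority costs no alpha, and both superiority tests must pass.** Both statements are right. A reader might infer that the superiority step needs its own adjustment, or that the two superiority tests need splitting. The documents support neither. But these protections cap the safety branch only and say nothing about its union with the secondaries.

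2. **No study-wide error rate is stated.** This also stands. The plan does not break a familywise level that it set for itself. The point is that its hierarchy and Hochberg steps aim at control and leave out one formal claim.

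3. **The adverse case is remote.** It needs no change in one safety endpoint together with a subgroup that does not benefit. Pilot changes were −15.0 and −12.6 points out of range, and +30.7 in range in the heavier pilot group. A reader might infer that the error rate simply doubles to 5%. It does not: 5% is a worst case that needs SDs below those in Tables 1 and 2, and at pilot effects there is no type I error to inflate. However, the pilot tables stop at 2500 g, while the upper weight group is 2501–3500 g, so the documents hold no data on the subgroup concerned.

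4. **Sequencing is not free.** This stands. In the simulated adverse case at Table 1 SDs, the true lighter-group claim is made in 81% of trials as written and about 2% with superiority placed second. With a true 3-point reduction in time below range (SD 10.8, n = 40), that superiority test passes only about 40% of the time. Section I itself cites an automated-control trial with more time at 80–86%. The order is a real choice for the sponsor.

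**Conclusion.** The gap holds on the text: two formal sets of claims each take the full one-sided 0.025 from the same non-inferiority results, unordered and unsplit. Counting one secondary objective, the chance of a false claim is bounded by 0.05. It is about 3.7% at the Table 1 SDs with correlation −0.75 and approaches 5% with smaller SDs, in the adverse case only. These sizes rest on normal differences, assumed 23/17 weight groups, and time in range mirroring time out of range. The last is approximate: Table 1's mean changes are 28.4 in range against 15.0 + 12.6 = 27.6 out of range.

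A reader might go further and count three branches, with a bound of 0.075, by treating the two secondary objectives as parallel. The documents call the testing hierarchical and number the objectives, but do not say whether objective 2 depends on objective 1, so that reading is not established. It does mean that the remedy must order them, or 0.025 is not secured.

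This should be settled before analysis. It concerns the additional claims, not the primary result.

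**What to change.** In the opening of Section V, state one fixed sequence at one-sided 0.025:

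1. both safety non-inferiority tests and the performance test;
2. both safety superiority tests;
3. secondary objective 1, with Hochberg across the weight groups;
4. secondary objective 2, with Hochberg across the skin groups, only if both groups in objective 1 pass.

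Amend the Primary Safety Objective so that superiority is tested at step 2. It would then also depend on the performance test, which it does not now.

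If the sponsor values the subgroup claims more, safety superiority can go last, tested only if all four group tests pass. That is demanding: overall sample size is driven by the weight groups and not by skin, and Munsell value 6 falls in neither skin group.

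**Cost.** A few sentences and no extra infants. Splitting alpha 0.0125/0.0125 instead would need 44 evaluable infants for 95% power per safety superiority test by the plan's method, against 40 planned. The downside of any sequence is that later claims fall with an earlier failure. With superiority second, this is unlikely at the pilot or planned effects and likely if time below range does not improve.
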